2 PROTOCOL SUMMARY

This study was a multicenter, randomized, controlled, open-label, parallel group study.

Approximately 100 patients were planned to be randomized and treated in a 1:1 ratio between treatment groups. A total of 43 patients were randomized and 40 patients treated at the time of enrollment and study termination. At the time of study termination 21 of the 40 patients treated received Varithena treatment.

This study was performed by qualified and licensed Investigators at 9 sites located in the United States.

This study collected evidence on patient reported outcomes of Varithena compared to Endothermal Ablation (ETA) when used to treat the incompetent Great Saphenous Vein (GSV). ETA will include either Radiofrequency ablation (RFA) or Endovenous laser ablation (EVLA) according to the site's standard practice. This study planned to provide long term (1-year, 2-year, and 3-year) outcomes.

2.1 Study treatment

After consenting and meeting all inclusion criteria and none of the exclusion criteria (I/E), patients were randomized to either Varithena (test) or ETA (control). The Electronic Data Capture (EDC) system was used to assign subjects to the test or control treatment group. Commercially distributed Varithena (polidocanol injectable foam) 1% (Approved 25 Nov 2013 NDA 205098) was administered by intravenous injection using ultrasound guidance, administered via a single cannula into the lumen of the target incompetent trunk veins or by direct injection into varicosities as described in the United States Prescribing Information (USPI).

2.2 Study Population

This study was designed to collect comparative evidence on patient reported outcomes of Varithena compared to ETA when used to treat patients experiencing symptoms of superficial venous incompetence of the GSV, defined as reflux > 0.5 seconds on duplex ultrasound in a single limb. Data was collected on 43 randomized and 40 treated patients at 9 investigational sites in the United States.

2.3 Data collection schedule and assessments

SCHEDULE OF VISITS

Procedure/Assessment	Screening/ enrollment	Index procedure (Treatment)	Follow-up Visits					
			7 days post procedure (± 3 days) office visit	3 months post procedure (± 14 days) office visit	6 months post procedure (± 14 days) office visit or telephone	12 months post procedure (± 30 days) office visit	24 months post procedure (± 30 days) office visit	36 months post procedure (± 30 days) office visit
Informed consent process	X							
Demographics	X							
Medical history	X							
Physical examination	X							
Duplex ultrasound	X		X	X		X	X	X
Mapping of superficial and deep veins	X							
Randomization	X							
Varithena or ETA procedure		X						
VVSymQ	X		X	X	X	X	X	X
VEINES-QOL/sym	X		X	X	X	X	X	X
rVCSS	X		X	X	X	X	X	X
EQ-5D	X		X	X	X	X	X	X
CEAP Clinical Classification	X		X	X	X ¹	X	X	X
Adverse event assessment		X	X	X	X	X	X	X

¹Performed only if patient returns for office visit

3 ENDPOINT ANALYSIS

Hypotheses

There was no pre-specified formal hypothesis relating to the comparison between treatment groups.

Sample Size

Approximately 100 patients were planned to be randomized and treated in a 1:1 ratio between treatment groups to allow for a minimally detectable absolute difference of 2.0 points, assuming a standard deviation of 5.0 points in both arms.

The assumption for the standard deviation was based on baseline standard deviation values observed in the Vanish 1 and Vanish 2 studies (4.96 and 4.55, respectively).

Statistical Methods

3.1 Safety Analyses

Adverse Events

Adverse Drug Reaction (ADR) / Serious Adverse Drug Reaction (SADR) related to Varithena were documented from the start of the index procedure through the latest completed visit prior to study termination, the latest subject visit being the 12-month visit at the time of termination. In addition, only SAE related to ETA or to the procedure were to be documented from the start of index procedure through the original planned 36-month follow up timeframe.

Adverse events were coded according to Medical Dictionary for Regulatory Activities (MedDRA) the current version and will be reported by system organ class (SOC) and preferred term (PT). The MedDRA version used for reporting the study will be the version used for coding the trial and will be specified in the clinical study report and as a footnote in the related outputs.

The Investigator or physician sub-Investigator determined the seriousness of each AE and whether it is Varithena, ETA, or procedure related.

The following summaries will be provided by treatment and total:

- Overall summary of AEs
- All AEs by primary SOC and PT
- AEs suspected to be related to procedure and/or device by primary SOC and PT
- AEs by primary SOC, PT and worst severity
- AEs leading to study discontinuation
- Most frequent AEs ($\geq 5\%$) by primary SOC and PT

AEs will be summarized by presenting the number and percentage of patients having at least one AE, having at least one AE in each primary SOC and for each PT. A patient with multiple occurrences of an AE will be counted only once in the category.

There were no SAEs reported at the time of study termination.

Partial dates will be imputed using the rules defined in [Appendix 7.1](#).

All AEs reported in the database will be listed with the SOC, PT, and investigator's Verbatim terms.

Deaths

There were no patient deaths reported at the time of study termination.

GENERAL STATISTICAL METHODS

The statistical analyses will be performed on the analysis datasets with appropriate software, SAS® Software version 9.4 (SAS Institute, Cary, N.C.).

Continuous data will be summarized with means, medians, standard deviations, quartiles (25th and 75th) minima and maxima, unless otherwise specified. Categorical data will be summarized with observed counts and percentages for each category. Unless otherwise specified, the percentage denominator will be the number of patients in the analysis population.

In case of subcategories, the relative frequencies will be calculated on the bases of the patients in the respective category; in this case a footnote will be added explaining the different denominators.

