8.1.2 Recording Adverse Events

ADR/SADR related to Varithena will be documented from the start of the index procedure through 36-month follow up. In addition, only SAE related to ETA or to the procedure will be documented from the start of index procedure through 36-month follow up. ADR/SADR/SAE should be managed as discussed in Section 8.3.

At any time during the study, the patient may volunteer information that resembles an ADR/AE. In this study, patients should be encouraged to report spontaneously or in response to general, non-directed questions. Once it is determined that an ADR/AE has occurred, the Investigator or physician sub-Investigator should determine if the ADR/AE meets seriousness criteria and is related to Varithena, to the ETA device, or to the procedure according to Section 8.1.1. Any medical management of an event and the date of resolution of the event must be recorded in the source document and on the appropriate eCRF using medical terminology according to Sponsor instructions.

For each related ADR/SADR/SAE, the following information will be recorded:

- ADR/AE term
- Serious criteria
- Severity
- Action taken

Owner(s): [name]

- Relevant concomitant medications
- Relevant laboratory/test data
- Relationship to study treatment
- Expected/Unexpected
- Date of onset
- Outcome and type of resolution (with/without sequelae)
- Date of resolution

Once the patient has been discharged from the study, the Investigator has no obligation to seek further follow-up with the patient in order to identify new ADRs/SADRs/SAEs. However, if the Investigator becomes aware of an ADR/SADR/SAE that has occurred following the patient's discharge from the study and the Investigator considers the ADR/SADR/SAE has reasonable possible relationship to Varithena or is possibly, probably, or definitely related to the ETA device, then the Investigator should report the SADR/SAE as described in the protocol.

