8.4 Periodic Safety Reporting

ADRs/SADRs/SAEs will be recorded on the AE form and the severity graded using NCI CTCAE version 5.0. The Investigator or physician sub-Investigator will judge the seriousness of each AE and whether it is Varithena, ETA, or procedure related.

Periodic safety reports prepared by the Sponsor will be distributed across all study centers. The Investigator will be responsible for informing the IRB.

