9.5 Safety Analyses

Procedure and treated leg related AEs and SAEs will be coded and summarized for each of the treatment groups. Number of patients and number of events will be displayed for each body system and event term.

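### Non-serious events are to be recorded only if attributed to Varithena, so the SAP's AE tables by treatment and total are not comparable between arms and the ETA column is expected to be empty or incomplete

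*SAP*

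**What the plan says.** Protocol 8.1.2 sets two recording scopes according to the cause to which an event is attributed. For the drug: "ADR/SADR related to Varithena will be documented from the start of the index procedure through 36-month follow up". For the comparator and the procedure: "only SAE related to ETA or to the procedure will be documented from the start of index procedure through 36-month follow up". Protocol 8.4 describes the AE form in the same terms: "ADRs/SADRs/SAEs will be recorded on the AE form and the severity graded using NCI CTCAE version 5.0". Because 8.1.1 defines an ADR as a response to a drug, that list has no category for a non-serious event caused by ETA.

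SAP 3.1 carries the rule forward: "In addition, only SAE related to ETA or to the procedure were to be documented from the start of index procedure". It then introduces its AE tables: "The following summaries will be provided by treatment and total". These include an overall summary, all AEs by system organ class and preferred term, AEs by worst severity, and AEs at or above 5%. The general methods text takes the analysis population as the default percentage denominator. The section also states: "There were no SAEs reported at the time of study termination".

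Other text is broader. Protocol 9.5 promises: "Procedure and treated leg related AEs and SAEs will be coded and summarized for each of the treatment groups". Protocol 7.2.3 has AEs recorded at follow-up visits in either arm, 7.3.12 has the investigator assess all AEs, and 8.3 requires ADRs as well as SAEs related to Varithena, the ETA device or the procedure to be reported on the AE form.

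**The concern.** A by-arm AE table can be read as a comparison only if the same kinds of event were sought and recorded in both columns. Here a non-serious event qualifies if it is attributed to Varithena. A similar event after ETA does not qualify unless it is serious. Printed side by side under an all-AE title, an uncollected event looks like an event that did not happen. A reader could conclude that Varithena causes harms that ETA does not, or that ETA was event-free, and the data could support neither conclusion.

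SAP section 1 drops the primary and secondary endpoint analyses after early termination. The AE tables are therefore the main comparative outcome results left in the abbreviated study report and the ClinicalTrials.gov posting, where a 0% entry would stand as data.

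**Working it through.** The plan gives no AE rate or AE-related figure to reproduce. The check applies the recording rule to the planned tables and then sizes the distortion under stated assumptions.

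**Inputs**
- Treated patients: 40, of whom 21 received Varithena (SAP section 2). ETA = 40 − 21 = 19.
- Recordable events: Varithena-related reactions of any seriousness; for ETA or the procedure, related SAEs only (protocol 8.1.2, SAP 3.1).
- SAEs reported: 0 (SAP 3.1).
- Denominators: 21, 19 and 40 (as-treated population).

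**Step 1: expected content of the ETA column.** Eligible ETA events are related SAEs, and none was reported. If the rule was followed, each AE table shows 0/19. This needs both the rule and the observed absence of SAEs. At an assumed related-SAE rate of 1%, 2% or 5% per patient, the chance of none in 19 is 0.99^19 = 83%, 0.98^19 = 68% or 0.95^19 = 38%, so the rule alone does not force an empty column.

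**Step 2: the total column.** If k Varithena patients have a recorded reaction, their arm shows k/21 and the total shows k/40, a reduction by the factor 21/40 = 0.525. With k = 6 (assumed), 6/21 = 28.6% becomes 6/40 = 15.0%.

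**Step 3: how far a printed zero could mislead.** Assume the same true non-serious event rate p in both arms, recorded in the Varithena arm alone.

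| Assumed p | Expected recorded, Varithena (21p) | Expected affected, ETA (19p) | Recorded, ETA | Chance of a true zero in ETA, (1 − p)^19 |
|---|---|---|---|---|
| 10% | 2.1 | 1.9 | 0 | 13.5% |
| 20% | 4.2 | 3.8 | 0 | 1.4% |
| 30% | 6.3 | 5.7 | 0 | 0.1% |

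**Step 4: what a reader might compute.** None of this is a planned output.
- Exact two-sided 95% upper limit for 0/19: 1 − 0.025^(1/19) = 17.6%. It would look like evidence about ETA although non-serious ETA events were outside the rule.
- Fisher's exact test, 6/21 against 0/19: [C(21,6) + C(19,6)] / C(40,6) = (54,264 + 27,132) / 3,838,380 = 0.021.
- Five patients are enough to cross 0.05 (5/21 against 0/19 gives p = 0.049). With equal true rates of 20% or 30%, one-sided recording would produce p < 0.05 in 41% or 80% of such trials, against about 3% with symmetric recording.

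**The case against.** The strongest counter-argument is that the documents do not settle what was entered. Protocol 7.2.3, 7.3.12, 8.3 and 9.5 could lead a site to enter non-serious ETA or procedure events. The SAP was written after termination, when the absence of SAEs was known, yet it plans a table of AEs related to the procedure and/or device. That is consistent with such events being in the database, although it may be template text. This objection stands. A reader might infer that the ETA column is zero by construction, and the documents do not support that. The zero is expected if 8.1.2 was followed and rests also on no SAEs having been reported. Partial entry that varies by site would not rescue the comparison, because the column would then be incomplete to an unknown degree.

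A reader might also infer that non-serious events are recorded only in the Varithena arm. The rule follows attributed cause, not arm. A non-serious event attributed only to the procedure falls outside it in both arms. Protocol 6.1.2 also allows additional veins to be treated by another modality after the 3-month timepoint, so an ETA patient could later contribute a Varithena reaction.

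It is equally too strong to say that unrelated events are never recorded. Protocol 8.3 sends events unrelated to Varithena or the procedure to the complaint process, but 8.2 leaves other documented events to periodic study reporting.

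Finally, the tables are descriptive, SAP section 3 states no formal comparative hypothesis, and SAP 3.1 states the rule above the table list. This limits the formal consequences. It does not help someone who sees only the printed table or the registry entry.

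**Conclusion.** The concern holds in this form. As written, the plan records non-serious events only if attributed to Varithena and then sets the arms side by side with no caveat on the tables. The ETA column (N = 19) is expected to be empty, or incomplete if some sites followed the broader wording. Under either reading, the all-AE, worst-severity and frequent-AE tables are not comparable between arms, the total column (N = 40) is not an AE rate for all treated patients, and the all-AE label misdescribes the content.

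The dilution factor of 0.525 follows from the patient counts if all recorded events come from the Varithena arm. The 6/21 count, the 10% to 30% event rates and the SAE rates are assumptions, because the documents give none. The 17.6% limit and p = 0.021 show only what a reader could derive from the printed table. The documents establish the asymmetry of the rule. They do not establish an actual 0/19, which only the AE database can show.

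**What to change.** Amend SAP 3.1 before the tables are produced:

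1. Reconcile protocol 8.1.2 and SAP 3.1 with protocol 7.2.3, 7.3.12, 8.3 and 9.5. Check the AE database, and state which kinds of event were actually collected in each arm.
2. If no non-serious ETA or procedure events were collected, present Varithena-related reactions for the Varithena arm only (N = 21), show ETA as *not systematically collected* rather than 0%, and drop the total column. Keep the by-arm display for related SAEs and deaths. If some such events were entered, list them and flag them as incompletely ascertained; do not suppress them.
3. Retitle the all-AE table to match what was recorded.
4. Footnote the differing collection rule on every AE table and repeat it in the registry's AE description.

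The order matters: marking ETA as not collected before looking at the database could hide or misdescribe real entries. The cost is a database check plus changes to SAP wording, table shells and footnotes. The downside is the loss of an apparently complete two-arm AE table. The by-arm display that remains may cover only categories already reported as zero.

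### The SAP's only relatedness-based AE table does not name Varithena, so it can omit non-serious Varithena reactions

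*SAP*

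**What the plan says.** SAP 3.1 lists six AE summaries by treatment and total. Only one is selected on relatedness: "AEs suspected to be related to procedure and/or device by primary SOC and PT". A few lines earlier, the same section says the investigator judged for each AE "whether it is Varithena, ETA, or procedure related", which is a three-way attribution.

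On what is collected, SAP 3.1 says that "Adverse Drug Reaction (ADR) / Serious Adverse Drug Reaction (SADR) related to Varithena were documented from the start of the index procedure", and that "only SAE related to ETA or to the procedure were to be documented from the start of index procedure". Protocol 8.1.2 has the same rule: "ADR/SADR related to Varithena will be documented from the start of the index procedure through 36-month follow up", followed by "In addition, only SAE related to ETA or to the procedure will be documented from the start of index procedure through 36-month follow up". SAP 3.1 also states: "There were no SAEs reported at the time of study termination".

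In Protocol 8.1.2, 8.2.1 and 8.3, *device* in causality wording means the ETA device, and Varithena is listed beside it as a separate item. Protocol 6.1.1 and SAP 2.1 identify Varithena as a product approved under an NDA, and its reactions are handled as ADRs and SADRs.

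**The concern.** The table's selection rule does not match the attribution scheme in its own section. It uses two categories where the plan has three, and the category left out is the test product. A non-serious reaction judged to be caused by Varithena, and not also attributed to the procedure, meets the recording rule but not the table's rule.

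This matters more because the study was stopped. SAP section 1 drops the primary and secondary endpoint analyses and limits the plan to an abbreviated CSR and ClinicalTrials.gov, so the safety tables are a main part of what remains. A reader looking for treatment-related events will go to this table. No other planned output is specified to show attribution to Varithena: the AE listing is described only by SOC, PT and verbatim term.

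**Working it through.** No arithmetic decides this point and the plan gives no figure to reproduce. The check is to take each class of event the documents mention, ask whether it had to be recorded (Protocol 8.1.2, SAP 3.1), and test it against the literal wording of the table.

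| Event class | Recording required? | Enters the table as worded? | Reported at termination? |
|---|---|---|---|
| Non-serious Varithena ADR | Yes | Only if also attributed to the procedure | Not stated |
| Varithena SADR | Yes | Only if also attributed to the procedure or ETA device | None (no SAEs) |
| ETA-related SAE | Yes | Yes | None (no SAEs) |
| Procedure-related SAE | Yes | Yes | None (no SAEs) |
| Non-serious ETA or procedure event, not Varithena-related | No | Yes, if a site entered one | Not stated |

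1. *Which required events can exist.* With no SAEs, rows two to four are empty. Row five was not required. That leaves row one, the non-serious Varithena ADRs, as the only required events the table could hold.

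2. *Whether row one is sure of a place.* Protocol 8.2 first asks a yes/no question about Varithena, then adds an assessment against the procedure and ETA, and states that addition for SAEs. Protocol 8.1.2, Protocol 8.4 and SAP 3.1 suggest that all three relationships are considered for every AE. Protocol 8.1.2 lists a single item for relationship to study treatment among the data to be recorded. Inclusion is therefore possible but not assured.

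3. *Whether drug and procedure are distinct.* Protocol section 10 refers to SAEs related to the product or to its procedure as alternatives, so one attribution does not imply the other.

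4. *How many patients are exposed to the gap.* SAP section 2 gives 40 treated, 21 with Varithena, which leaves 40 − 21 = 19 with ETA. The gap concerns the 21.

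5. *How many events.* The share of non-serious Varithena ADRs left out runs from none (all also attributed to the procedure) to all (none so attributed). The documents give no event counts or attributions that would narrow this.

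**The case against.** The strongest reply is that the events are not lost. The other five summaries in SAP 3.1 (overall, all AEs, worst severity, discontinuation, and the most frequent) are not filtered on relatedness, and every AE in the database is listed. Because every non-serious event that had to be recorded is Varithena-related by rule, the Varithena column of the all-AE table already shows these reactions. This stands, and it limits the fault to one table.

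A second reply is that the wording may have been meant broadly. The protocol speaks of a Varithena procedure. Several of the common reactions in Protocol 8.5 are injection- or infusion-site events that an investigator could readily attribute to the procedure as well. Protocol 6.1 also describes the canister as a device. The first two observations make exclusion uncertain, so the table *can* omit these events; the documents do not show that it will. The canister remark is a product description, and no causality text defines *device* to include Varithena. If that was the intent, the bullet should say so, because SAP section 5 gives the analysis and validation to a CRO. The table shells are in a separate mock-up document that is not available here, so they cannot settle the matter.

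A reader might also blame this bullet for an ETA column with no required events. That follows from the recording rule, which takes ETA and procedure events only if serious, together with the absence of SAEs. Rewording the bullet would not change it.

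**Conclusion.** The point holds as a defect in one table. Read literally, SAP 3.1's only relatedness-based AE table need not contain the non-serious Varithena ADRs, which are the only required events it could hold given that no SAEs were reported. It could understate treatment-related events in the Varithena arm, or be empty while such reactions exist. The number affected is unknown.

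This rests on two readings: that *device* in the bullet means what it means in the protocol's causality text, and that a reaction can be attributed to Varithena without also being attributed to the procedure. The documents support both.

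Three stronger conclusions might be inferred, and the documents do not support them. Varithena reactions are not the only events the study records, since SAEs related to ETA or the procedure were also required. Harm is not hidden from the report, since the unfiltered summaries and the listing keep these events. And although Protocol 9.5 has a similar gap ("Procedure and treated leg related AEs and SAEs will be coded and summarized for each of the treatment groups"), it does not need amending: the terminated study is reported under the SAP, so a protocol change would not alter any output.

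**What to change.** Replace the SAP 3.1 bullet with: *AEs related to Varithena, to the ETA device, and/or to the procedure (any, and each attribution separately where recorded) by primary SOC and PT.* Add a footnote that non-serious ETA- and procedure-related events did not have to be recorded, so the arms are not comparable in this table.

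The qualifier *where recorded* is needed because the eCRF is not among the documents, and separate procedure and ETA attributions for non-serious events cannot be confirmed. If they were not captured, the table can still show relation to Varithena and say that the rest is unavailable.

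The cost is one bullet, one footnote and the matching table shell. SAP 3.8 already provides for revising the plan before the analyses are run. No new data are needed for the combined any-attribution version, and Protocol 9.5 can stay as it is.

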8.3 Submitting Safety Reports

ADR, SAE, SADR, or SUSAR related to Varithena, the ETA device, or procedure must be reported to the Sponsor or its designate by completing the Adverse Event form in the eCRF. SAE, SADR, SUSAR related Owner(s): **[name]**

to Varithena, the ETA device, or procedure must be reported within 24 hours of becoming aware of the event. If the EDC is not available, the Investigator or other study site staff reports the event to the appropriate Sponsor representative by email to the study-specific mailbox. The Sponsor representative will advise the Investigator/study site staff how to proceed.

The Adverse Event form provided in the eCRF should be completed and signed by the Investigator or physician sub-Investigator. The entire Adverse Event form needs to be completed, if possible, to keep requests for additional information to a minimum. Patients experiencing ADR, SAE, SADR or SUSAR should be followed clinically and with laboratory studies, if appropriate, until medical treatment and/or medical monitoring of the event is no longer required because the event resolves or stabilizes, returns to baseline if a baseline value is available, can be attributed to agents other than the study treatments or a referral for appropriate follow-up care has been made.

The Investigator must promptly inform the IRB of all SUSARs needed per IRB requirements. These events will be reported by the Sponsor as appropriate to the regulatory authorities. The Investigator will receive notification of these events across all study centers from the Sponsor.

ETA safety reporting must follow the direction for use and the commercial complaint reporting process as appropriate for each specific device.

AE/SAE unrelated to Varithena or the procedure should be directly reported to [contact] as according to the Varithena commercial complaint reporting process.

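### The SAP's statement that no SAEs were reported supports only a zero of related SAEs, because the protocol's recording rule is not carried into that sentence or the AE table titles

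*SAP*

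**What the plan says.** The statement at issue is in SAP 3.1: "There were no SAEs reported at the time of study termination". The opening paragraph of the same section gives the recording rule. For the test product, "Adverse Drug Reaction (ADR) / Serious Adverse Drug Reaction (SADR) related to Varithena were documented"; then "In addition, only SAE related to ETA or to the procedure were to be documented". This follows Protocol 8.1.2, which says that "ADR/SADR related to Varithena will be documented from the start of the index procedure through 36-month follow up" and continues, "In addition, only SAE related to ETA or to the procedure will be documented".

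Protocol 8.3 sets the reporting routes. Its first paragraph puts events related to Varithena, the ETA device or the procedure on the eCRF Adverse Event form, with 24 hours allowed for serious ones. A later paragraph says "ETA safety reporting must follow the direction for use and the commercial complaint reporting process as appropriate for each specific device". The last paragraph begins "AE/SAE unrelated to Varithena or the procedure should be directly reported to" and names the Varithena commercial complaint process as the route.

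SAP 3.1 also plans an overall AE summary, a table of all AEs by system organ class and preferred term, and a listing of the AEs held in the database. It plans no SAE table. SAP section 1 says that these outputs serve the abbreviated CSR and ClinicalTrials.gov.

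**The concern.** Protocol 8.1.1 defines an SAE by its outcome or seriousness, whatever the cause. A reader of the abbreviated CSR or the registry entry who sees that there were no SAEs will take it in that sense: no serious event of any cause in either arm. The data collection was narrower. It rests on a relatedness judgement by the investigator in an open-label study, and the planned SAE statement does not mention that filter.

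This matters more than usual here. SAP section 1 drops the primary and secondary endpoint analyses after early termination, so safety is most of what remains to be reported by treatment group.

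**Working it through.** The zero is an observed count with no formula behind it, so there is nothing to recompute. The check is to ask, for each kind of SAE, whether following the protocol would bring it into the count in SAP 3.1.

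**Inputs.** SAP section 2: 43 randomized, 40 treated, 21 of them with Varithena, so 40 − 21 = 19 with ETA. SAP 3.1: SAEs reported = 0.

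**Routes, set side by side.**

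| SAE judged related to | Protocol 8.1.2 | Protocol 8.3 | Covered by the zero in SAP 3.1? |
|---|---|---|---|
| Varithena | Documented | eCRF, within 24 hours | Yes |
| The procedure | Documented | eCRF, within 24 hours | Yes |
| The ETA device only | Documented | eCRF by the first paragraph; device complaint process by a later one; Varithena complaint process by a literal reading of the last, which does not mention ETA | Yes, if the first paragraph was followed |
| None of these | Not provided for | Varithena complaint process | Not shown |

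**Does anything bring the last row back into the study data?**

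- Protocol 7.3.12 has the investigator assess all AEs for relationship, but assessing an event is not the same as recording it under 8.1.2, which asks for event details on related events.
- Protocol 8.2 sends other events to periodic reporting, but only those already documented in the study.
- Protocol 11.2.1 requires every AE to be recorded, but as the protocol applies, which leads back to 8.1.2.
- Protocol section 10 requires SAE reconciliations to be resolved before the database is declared clean. It does not say which sources are reconciled and does not mention complaint records. The safety-database entry described there is again limited to SAEs related to Varithena or its procedure.

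None of these clearly overrides 8.1.2 and 8.3.

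**Result.** The supported statement is 0 SAEs judged related to Varithena, ETA or the procedure among 40 treated patients. The all-cause count cannot be determined from the documents. A binomial bound on 0/40 would not help: it would describe the sample size, not the category of event that the count leaves out.

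**The case against.** There is a good case on the other side, and much of it stands.

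- *The section already states the rule.* It does, in its first paragraph, and the sentence itself says reported. Protocol 4.5 also lists related SAEs as the assessment, so the zero answers the question the protocol set. But the sentence and the table titles can travel to the CSR and the registry without that paragraph.
- *Related-only collection is a legitimate choice for a marketed product in Phase 4.* Agreed. The point is how its result is labelled.
- *Nothing expressly bars unrelated SAEs from the eCRF.* True. The causality criteria in 8.2.1 include a not-related category, and the SAP plans both a table of all AEs and a separate one of related AEs. The eCRF is not among the documents. That unrelated SAEs stayed out of the database is a strong inference, not a stated fact.
- *The ETA paragraphs in 8.3 need not conflict.* The device complaint sentence can be read as an extra duty on top of the eCRF. The missing mention of ETA in the last paragraph is then a drafting ambiguity, which still needs to be reconciled.

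A reader might go further and infer that a diverted SAE leaves no trace and can never be checked. The documents do not support that. Source records are kept and open to monitors and auditors (Protocol 11.5 and 11.11), and complaint reports are themselves a record. Because the recipient of those reports is masked, the documents cannot show that the sponsor was bypassed.

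**Conclusion.** The concern holds as a labelling fault in SAP 3.1. The zero, for 40 treated patients in both arms, is a zero of related SAEs and is not shown to be an all-cause zero. The titles of the overall AE summary and the all-AE table have the same gap.

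A reader might infer that serious events occurred and were left out. Nothing in the documents says so, and the true all-cause count may be zero. The statement of no deaths is less exposed, because SAP 4.4 records death as a disposition category whatever its cause.

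The conclusion assumes that sites followed 8.1.2 and 8.3 as written and that the SAE reconciliations in Protocol section 10 did not extend to complaint records. If the sponsor can show otherwise, an unqualified zero could be justified.

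**What to change.** In SAP 3.1, replace the sentence with: *No SAEs judged related to Varithena, ETA or the procedure were recorded; unrelated SAEs were not systematically collected in the study database.* Put the same limit in the AE table titles or footnotes and in the registry entry. SAP 3.8 already provides for documenting such a change in a SAP revision before the analyses.

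If an all-cause SAE count is to be reported, first reconcile the available complaint records, source documents and exit forms for the 40 treated patients before the final snapshot, and list any SAE found. This assumes that the complaint records exist and can be linked to study patients.

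Reconcile the paragraphs of Protocol 8.3 on where an SAE related only to the ETA device is reported, so that it is clear whether the related-SAE zero covers such events.

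Changing prospective collection would serve no purpose, since enrollment and follow-up have been terminated. The wording change costs a few lines of text. The reconciliation, if chosen, is a one-off check of 40 patients and could make the safety statement less favourable.
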